3.3 Stakeholder involvement

Two veteran charities have been involved in the development of the research questions and methods to support participant recruitment and retention. Charity members reported that NLP therapy is perceived as effective in the ex-service community, and consequently they thought our recruitment targets were realistic. The stakeholder group are advisers from the target population who have some experience of PTSD and who are currently well. They are not research participants but are patient and public involvement advisors. We will follow Involve guidelines on working with these stakeholders in relation to reimbursement for their time and expenses to participate.

We propose two stakeholder activities, a major one involving veterans and family members and a second involving veteran charities.

3.3.1 Veteran and family member stakeholders

[name], Professor of Psychological Trauma & Mental Health, and her team will lead the engagement (PPI) with NI veteran communities. An Involvement team of 10 individuals who have experienced and recovered from PTSD and a significant other will be recruited via (Ret) Major [name], Director of the UDR and Royal Irish Armed Forces After Care Service, Northern Ireland. This service has wide reach and we will recruit members from throughout the UK. Members will be offered £50 expenses for each of six involvement meetings. They will develop lay language surrounding the

NLP/RTM intervention, design study information methods to optimise transparency and reach, support project management challenges, review findings and support dissemination. See appendix 2 for full details.

We have designed stakeholder involvement with diversity and inclusion at the forefront of our planning. This funded involvement team will support the development of a web site, hosted by Inspire, which will use videos and written text to communicate study information consistently and transparently to the UK veteran community. It will take account of literacy, health literacy and mental health stigma issues that may challenge the target population. It will be veteran population-facing to encourage these communities to engage with it and to offer the widest possible reach and access to the research opportunity. The involvement of the UDR and Royal Irish Armed Forces After Care Service field teams in the involvement group will facilitate a great deal of person to person information flow through the regional communities with the project website as a backstop for ensuring core information is communicated consistently to potential participants and their families.

3.3.2 Charity sector stakeholders

We will establish a stakeholder group of four UK-based charity representatives to engage with electronically and in-person throughout the research to ensure the views of the veteran charity sector are represented. The two charities who initially approached us with interest in taking part in research, *Veterans at Ease* and *Healing the Wounds* will be invited to participate. A further charity has since approached us *Rock2Recovery*, and they will also be invited to participate. The fourth charity to be invited will be a major charity stakeholder in the UK such as *Combat Stress*. We are particularly interested in listening to the perspectives of smaller charities because they are the ones most often delivering unregulated NLP interventions that present both interest and a concern to the team. This group will meet by telephone conference on four occasions during the study. Meeting one will be to introduce them to the study and address any arising questions. It will close with an agreement of the focus of the three further meetings in relation to what issues the research team are experiencing that we may wish for their perspective on and the stakeholder interests in the ongoing study.

3.4 Ethical considerations

We propose the experimental evaluation of a novel psychological therapy in a vulnerable population and in the context of patient safety concerns from the community serving the target population. The ethical issues are therefore manifold and substantially centred around patient safety. Other ethical risks are whether full trial funding will be obtainable in the event of feasibility being demonstrated and patient safety risks determined to be acceptable, leaving a potentially effective therapy untested at scale. We have given careful consideration and consulted widely to establish these robust safety procedures to minimise any potential harm to participants.

To address the future funding issue, we have developed a careful project plan to maximise the likelihood of subsequent funding. Our exact choice of funder will be informed by upcoming deadlines and available themed calls in 2021. We outline two possibilities below. Upon successfully delivering on our external pilot study objectives we can apply to the HTA to undertake a phase III pragmatic trial as proposed above. The HTA have confirmed that this will be within their funding remit. Another option is to apply for an NIHR Programme Grant for Applied Research (PGfAR), a funding panel on which PI [name] sits and is therefore well placed to develop a competitive application. We are the only UK (and possibly international) team able to undertake a programme of research to robustly

investigate the potential benefits and harms of NLP informed mental health interventions. A PGfAR could propose the phase III trial and several of the following work packages:

- 1) A Phase III trial as proposed above;
- 2) Determine the mechanisms and moderators by which RTM exerts its effect;
- 3) Undertake an MRI study to detect hypothesised neurological changes during the RTM treatment;
- 4) Update the PI's 2012 systematic review on the effect and impact evidence for NLP interventions;
- 5) Undertake a feasibility study of an NLP intervention identified in the systematic review update that shows greatest clinical potential;
- 6) Complete qualitative research to understand NLP delivery training needs, patient safety issues and NHS commissioning pathways for the delivery of the RTM protocol and other NLP-based interventions within the NHS and the third sector.

3.5 Participants and Setting

The study takes place in the United Kingdom where collaborator Inspire (formerly The Northern Ireland Association for Mental Health) deliver PTSD treatment (37). Eligible participants will be exmilitary veterans presenting for treatment with a suspected diagnosis of PTSD or presenting for a second or subsequent time to services with a previously confirmed diagnosis of PTSD and where the participant has not responded to treatment. Eligibility will be determined during condition assessment and diagnosis by a consultant clinical psychologist in Inspire's clinical centre in Belfast who is fully qualified to confirm PTSD or complex PTSD diagnosis accordance to the DSM-5 using the Clinician Administered PTSD Scale (CAPS-5) and the ICD-TQ. The assessment will diagnose or confirm diagnosis. The first eligible 60 veterans who agree to participants will remain in the research trial for 52 weeks.

The diagnostic interviews will be undertaken by a trained consultant clinical psychologist at Inspire for this study. The diagnostic interviews are not routinely conducted by the charity Inspire but they do conduct a comprehensive, psychological clinical assessment supplemented by validated self-report screening questionnaires which includes: the Post-traumatic Stress Disorder Checklist for DSM-5 (PCL-5), the Patient Health Questionnaire (PHQ–9), the Generalised Anxiety Disorder (GAD–7), Comprehensive Outcome and Routine Evaluation-Outcome Measure (CORE-OM), a Therapy Assessment form (TA) and an End of Therapy Form (EoT). Therefore, we have taken the approach to have all PTSD or complex PTSD diagnosis (acute and/or chronic) to be confirmed by a qualified consultant clinical psychologist at Inspire in NI. We will not ask participants to complete duplicate scales at our baseline data collection if they have already been collected at the assessment stage.

3.5.1 Inclusion criteria:

1) Adults \geq 18 yrs. Women make up 10% of the UK Armed Forces and fewer than this experience combat-related roles. Therefore the majority of participants with a need for PTSD treatment will be males. However, the feasibility nature of this pilot requires that we understand whether the treatments and the research appeal to eligible female military veterans. We will therefore aim to recruit women to make up 10% of our sample.

2) UK military veterans from the Army, Royal Air Force of Royal Navy.

3) PTSD (acute or chronic) diagnosis determined by DSM-5 (38) using the Clinician Administered PTSD scale (CAPS-5) (39) during clinical assessment with an Inspire employed clinical psychologist.

4) Experiencing symptoms causing clinically significant distress or impact on social, occupational or other areas of functioning.

5) A history of exposure to one or more traumas.

6) Living or working in the UK.

7) Willingness to be randomised to either treatment.

3.5.2 Exclusion criteria:

1) Serving personnel.

2) Currently receiving psychological treatment for PTSD.

3) Currently has a comorbid DSM-5 mental health or personality disorder sufficiently severe as to intrude upon the participant's ability to cooperate with treatment.

4) Current dependence on alcohol as determined by an AUDIT 10 cut off of \geq 20 (41) or self-report of prescription or illegal substances dependence.

5) Participants who had a suicide attempt within the past month at time of recruitment.

6) Not able to provide informed consent.

7) Self-reported medication changes in the previous four weeks.

8) Unwilling to consent to audio-recording of all therapy sessions as a minimum requirement.

9) Any other documented reason in which the assessing Clinical Psychologists determine that treatment for other mental health symptoms takes precedent over their PTSD at the time of assessment.

3.6 Sample Size

The proposed external pilot sample size takes into account published recommendations for pilot trials (42, 43) which propose a method for determining an external pilot RCT sample size in order to minimise the sample size for the main RCT. This sample size will support the calculation of confidence intervals around the proportion of eligible participants who agree to take part in the research, and the attrition rates from both the treatments and the research. Our proposed sample size is 60, 30 in each arm. Initially, we had a 1:1 randomisation ratio. However, with 50% of our target randomisation figures achieved due to therapist attrition in the TF-CBT delivery arm we sought statistical advice and decided to change the randomisation ratio to 2:1 in favour of the experimental RTM. This would allow us to continue to recruit at the level required to fulfil our recruitment targets specified by our funder.

Treatment seeking in the veteran population is low (44, 45) and response rates to PTSD research invitations are poorly reported (46, 47). For example, Ulmer et al (2011) (48) screened 91 veterans with PTSD to recruit 22 participants to their pilot RCT. In a review of 7 randomised trials comparing TF-CBT with Eye Movement Desensitisation and Reprocessing, research and treatment attrition ranged from 8 - 58% with a mean of 29% (49). Taking these data into account, we propose to screen 180 people for eligibility, randomise 60 participants and expect an attrition of 30% and 50% (or lower) from the intervention and comparison respectively resulting in \geq 36 participants with data at 20 weeks follow up. A screening sample of 180 would be sufficient to obtain a 95% confidence interval for a

proportion of $\pm 8\%$ or narrower, and a sample of 60 for a 95% confidence interval of $\pm 13\%$ or narrower, both with 99.9% probability calculated using SAS POWER (50)

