3.12.2 Feasibility, acceptability, cost and safety outcomes

To determine feasibility we will collect data on numbers of eligible potential participants who are referred or self-refer for the study, the number of people who consent to participate and be randomised to either treatment and the number of people who remain in treatment and when people drop out and the number of people who remain in the research irrespective of whether they remain in treatment. We will calculate the cost of treatment by quantifying the number and duration of therapy sessions and by which therapist. This data will be collected by Inspire throughout the study duration using their Penelope data management system. We will include the cost of any patient safety measures used during treatment and up to the 20 week follow up point.

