Appendix 4. Progression criteria to a full non-inferiority RCT

Project	Measure of Success	Nature and number of	Timescale
Outcome 1:	In 14 months we identify 180 eligible	180 study participants	Months 5-18
Known rate of	narticinants		WOII(II3 J-10
trial			
recruitment,	Consenting and randomised	60 study participants	Months 5-18
retention in	participants $n = 60$		
treatment and	Treatment drop out:	>36 study participants	Months 5-21
research and	RTM protocol Intervention drop out ≤		
completeness	30%		
of outcome	TF-CBT intervention drop out ≤ 50%		
data assessed	Research attrition: Research follow up	36 study participants	At end of project
against our	retention 36 participants at 20 weeks		
green traffic			
light			
Outcome 2:	Baseline data set is complete for 90%	54 study participants	Months 5-18
Exploratory	of participants	54 study participants	WOIIIIIS 5-18
analyses of the	12 week follow up data set is complete	42 study participants	Months 8-21
outcome data	for 70% of study participants		
to support a	20 week data set is complete for 50%	30 study participants	At end of project
nower	of participants		
calculation for			
a fully powered			
non-inferiority			
trial.			
Outcome 3:	A trial adverse and serious adverse	All 60 trial participants	Month 2
Known safety	event definition and safety protocol is		
risks and	developed which identifies all		
amenorations	refers according to Inspire and		
ОГКПИТНЕГАРУ	research project-specific statutory care		
	pathways: contains adverse events (e.g.		
	relapse, hospital admission, suicide		
	and attempted suicide) across the 20		
	week follow-up period and		
	documented clinical actions taken to		
	mitigate participant risk		
	All adverse and serious adverse events	All 60 trial participants	Month 5-23
	and ameliorations recorded and every		
	event discussed at the bi-weekly		
	research team meeting.		
	A log of every adverse, serious adverse	All 60 trial participants	At end of project
	event and clinical and research team		
1	actions in response		

Outcome 4:	A minimum of 5 Inspire therapists will	The beneficiaries of an	Month 4
Establishment	complete the 20 hour masterclass and	expanded professional	
of expanded	be assessed as proficient in delivering	mental health capacity	
mental health	protocoled TF-CBT	across Northern Ireland	
care capacity	-	would be extensive.	
across	A minimum of 5 different Inspire		Month 4
Northern	therapists will complete the 70 hr RTM	Hitherto, TF-CBT has only	

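### The 20-week research-retention target of 36 equals the expected number of therapy completers, so this green light can be met without following up anyone who stopped therapy

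*Protocol*

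**What the plan says.** Protocol 3.6 fixes the size of the pilot ("Our proposed sample size is 60, 30 in each arm"). It then says the team "expect an attrition of 30% and 50% (or lower) from the intervention and comparison respectively resulting in" at least "36 participants with data at 20 weeks follow up". The sentence does not say whether this attrition is from treatment or from the research.

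Appendix 4, Outcome 1, has two separate rows:

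- **Treatment drop-out.** The limits are "RTM protocol Intervention drop out ≤" 30% and "TF-CBT intervention drop out ≤ 50" per cent, and the number attached is ">36 study participants".
- **Research attrition** ("Research attrition: Research follow up" and so on). The number attached is 36 participants at 20 weeks.

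Section 3.2(e) repeats the retention criterion as at least 36 at 20 weeks. It asks for at least 70% treatment completion in each arm, whereas Appendix 4 tolerates 50% drop-out in the TF-CBT arm.

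Elsewhere the protocol keeps leaving treatment and leaving the research apart. Section 3.12.2 will count "the number of people who remain in the research irrespective of whether they remain in treatment". Section 3.1 lists treatment and research attrition as rates to be determined, and 3.6 itself plans confidence intervals for both.

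**The concern.** If the number expected to have 20-week data is derived from treatment drop-out rates, the derivation treats everyone who stops therapy as lost to the research as well. A retention target set that way says nothing about whether people who stop can still be followed up.

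That question is central to the planned trial. A non-inferiority comparison needs outcomes on those who stopped therapy, and the protocol itself allows for unequal stopping in the two arms. As an illustration on assumed figures, suppose that in the main trial those who stop score 10 PCL-5 points worse at follow-up (range 5 to 20), and that none of them can be followed. A comparison of completers would then move the arm difference by (0.50 − 0.30) × 10 = 2 points (range 1 to 4), against the five-point margin expected in 3.14. A pilot whose green light does not look at follow-up after stopping could recommend a trial exposed to this.

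**Working it through.** **Inputs.** 60 randomised, 30 per arm (3.6). Attrition of 30% for RTM and 50% for TF-CBT (3.6). The same two rates as treatment drop-out limits (Appendix 4). At least 70% completion in each arm (3.2(e)). Allocation changed to 2:1 in favour of RTM after half the target had been randomised (3.6).

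**1. Reproduce the plan's figure.** Number = sum over arms of n × (1 − attrition) = 30 × 0.70 + 30 × 0.50 = 21 + 15 = 36. The match is exact. Other readings do not give it: a common 30% gives 60 × 0.70 = 42, the review mean of 29% cited in 3.6 gives 60 × 0.71 = 42.6, and a common 50% gives 30. A common 40% gives 36 only because it is the average of 30% and 50%.

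**2. Completers and stoppers implied by the plan's own limits.**

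| Basis | Completers | Stoppers | Share of completers needed to reach 36 with no stoppers |
|---|---|---|---|
| Appendix 4 limits, 30:30 | 21 + 15 = 36 | 24 | 36 of 36 (100%) |
| Appendix 4 limits, 35:25 | 24.5 + 12.5 = 37 | 23 | 36 of about 37 (97%) |
| 3.2(e), 70% in each arm | 0.70 × 60 = 42 | 18 | 36 of 42 (86%) |

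The 35:25 split assumes that 60 are reached: 15 + 20 = 35 to RTM and 15 + 10 = 25 to TF-CBT.

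**3. What the total would be if stoppers were followed** (30:30, drop-out at the Appendix 4 limits, all completers responding; the shares are assumptions): 0% gives 36, 25% gives 36 + 6 = 42, 50% gives 36 + 12 = 48, and 75% gives 36 + 18 = 54. The target sits at the zero end of this range.

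**4. What happens if some completers do not respond** (same basis). At 90% response, 32.4 completers give data, so 3.6 (about 4) of 24 stoppers are needed. At 80%, 28.8 give data, so 7.2 (about 7) of 24 are needed.

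**5. Whether another criterion fills the gap.** The 20-week completeness target in Appendix 4 is 50%, or 30 participants, which is lower still. The 12-week target is 70%, or 42. At the limits under 30:30 it would need 42 − 36 = 6 people who eventually stop. But it concerns an earlier time point, when TF-CBT (up to 18 weekly sessions, 3.11.2) may still be running, and it does not refer to people who stopped.

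**The case against.** Several points can fairly be made for the plan.

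- **The source of the rates is inferred.** Section 3.6 says only attrition, just after citing a review that pools research and treatment attrition, and it adds that the rates may be lower. It could be read as a cautious floor for data loss. This stands as a caveat. But the arm-specific rates and the total both match Appendix 4, where the rates are labelled as treatment drop-out, and a cautious floor would still not test follow-up after stopping.
- **The criterion is not met automatically.** A reader might infer that 36 is reached whatever happens to those who stop. It is not. At the limits under 30:30, every completer must respond within the window of 10 working days either side set in 3.13, and ordinary non-response would draw on stoppers (step 4). The supported statement is that it can be met without them.
- **The two rows are not one criterion counted twice.** A reader might infer this from the shared 36. The drop-out row is arm-specific and concerns therapy; the retention row is a trial total and concerns data. With 36 completers of whom 30 respond, and no stoppers followed, a trial meets the drop-out limits and fails retention. Heavy TF-CBT drop-out with good follow-up would do the reverse.
- **The estimates do not become completers-only.** A reader might infer that the SD and effect carried forward would come from completers. The documents do not support that. Follow-up irrespective of treatment is planned (3.12.2, 3.13), the PCL-5 is also taken at every session (3.12.3.1), and 3.14 specifies no completers-only analysis. A threshold does not decide which data are analysed.

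What remains is the threshold and how it was derived.

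**Conclusion.** The point holds in a limited form. The 20-week research-retention target is numerically the expected number of treatment completers at the drop-out limits in Appendix 4, although the protocol otherwise treats the two kinds of attrition as separate. The target can be reached with none of the 24, about 23 or 18 stoppers followed, depending on which of the plan's figures applies, and no other 20-week criterion covers them. This is a weak progression threshold, not an arithmetic error and not a defect in data collection.

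The conclusion assumes that the 3.6 rates are the Appendix 4 treatment limits and, for 35:25, that 60 are randomised. It does not rest on the 10-point illustration. Nor do the documents supply a required share of stoppers: 48 of 60, which corresponds to following half of them, is one value in a range, and it depends on the 30:30 split and on full response from completers.

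**What to change.** In 3.6, 3.2(e) and Appendix 4:

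1. Stop deriving the number with 20-week data from treatment drop-out. If 36 is kept, describe it as the expected number completing treatment under 30:30.
2. State research retention as its own criterion: 20-week PCL-5 obtained, counted over all randomised regardless of therapy status. Set the figure independently of treatment drop-out and for the amended allocation.
3. Report it by arm, and separately for those who completed and those who stopped therapy. Any minimum for those who stopped is for the sponsor to choose and justify.
4. Reconcile 3.2(e) with Appendix 4 on treatment completion in the TF-CBT arm.

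No new data are needed, because follow-up irrespective of treatment is already planned. The cost is that progression criteria would be revised after at least half of randomisation, and the green light may become somewhat harder to reach. If changing the threshold is resisted, the split report in item 3 alone would show what a total of 36 hides.

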3.7 Participant Recruitment

Potential participants will become aware of the study A) through Inspire's veteran mental health contracting organisations, a significant example being the RI & UDR Aftercare Service (ACS) and/or B) though our study public engagement work involving our traditional and online media announcements and those of veteran support organisations. Any eligible or ineligible person self-referring from a veteran support organisation will be encouraged, but not required, to inform that organisation of their engagement with the PETT team.

Pathway A: Described with reference to the Aftercare Service (ACS):

- 1. ACS caseworkers will inform clients with expressed mental health needs about the PETT study by sharing the PETT study invitation letter, a flyer containing a link to the information video, the PIS, the PCL-5 assessment form, a personal data processing consent form and a SAE. Interested potentially eligible participants return the completed forms to the research team via email or in the SAE. Due to Covid-19, ACS caseworkers are no longer conducting their assessments face-to-face so during this period and until face-to-face consultations are resumed they will now inform clients with expressed mental health needs about the PETT study during their phone consultations. They will share details about the study and signpost the potential participants to the study website for further information and provide contact details for the research team. In these circumstances, once a potential participant contacts the research team, a researcher will send them the flyer containing a link to the study information video, the participant information sheet, the PCL-5 assessment form and a personal data processing consent form via email. They will be invited to ask questions on the telephone or via email and if they wish to continue they will return the completed PCL-5 form and personal data processing consent form. They will also be given the opportunity to complete the PCL-5 and data processing consent form via a Qualtrics online link which can be sent to their mobile phone or email address.
- On receipt the researcher will score the PCL-5. If the person scores ≥33, they will be given the opportunity to ask questions in person, electronically or over the phone. If they wish to proceed the researcher will undertake informed consent in person, electronically or over the phone. Consent will be recorded in writing by wet ink, electronically or audio recorded.
- 3. If the person declines to participate or if their PCL-5 score is <32 and therefore screened ineligible to take part, the researcher will inform them of this and ask permission to inform ACS so their caseworker can proceed with appropriate referrals. Alternatively, the person will be invited to inform their caseworker directly. All personal data on these people will be shredded/electronically deleted.

- 4. Each participant will then self-complete baseline data collection with researcher support as needed in person, electronically or over the phone.
- 5. An appointment will be made for them with the Inspire Clinical Psychologist within two weeks to have a confirmatory PTSD diagnostic interview.
- 6. Once eligibility is confirmed they will be computer randomised to a therapy group and commence therapy within two weeks.
- 7. Those not eligible will be referred back to ACS by Inspire.

Pathway B) For all other recruitment routes

- 1. All public engagement, traditional and online social media announcements relating to the PETT study will contain the information video link and email address [contact].
- 2. Once a potential participant contacts the team they will be contacted by a named researcher who will offer the PETT study invitation letter, a copy of the PCL-5, a personal data processing consent form and the participant information sheet. They will be given the opportunity to ask questions and can complete the PCL-5 in person, over the phone or electronically. They will be made aware that if they experience distress in relation to completing the PCL 5, they can contact the researcher who can signpost them to support. Support organisations are also listed on the study invitation letter and in study emails.
- 3. If the person declines to participate or if their PCL-5 score is ≤ 32 they will be signposted to organisations, including Inspire and their GP, who they may wish to contact about further mental health assessment and treatment. In addition, if we know that they are currently being seen by a veteran charity organisation the person will be invited to inform the organisation or their caseworker directly. All personal data on these people will be shredded/electronically deleted.
- If the person's PCL-5 score is ≥ 33 the researcher will proceed to undertake informed consent in person, electronically or over the phone. Consent will be recorded in writing by wet ink, electronically or audio recorded.
- 5. The participant will then self-complete baseline data collection with the researcher support if needed in person, electronically or over the phone.
- 6. Following informed consent and baseline data collection an appointment will be made for them with the Inspire Clinical Psychologist within two weeks to have a confirmatory PTSD diagnostic interview.
- 7. Once eligibility is confirmed they will be computer randomised to a therapy group and commence therapy within two weeks.
- 8. For those ineligible the Clinical Psychologist will discuss, and signpost to other therapeutic options. If the participant is been seen by a veteran charity organisation they will be invited to inform the organisation or their charity caseworker directly.

Inspire receive on average 10-15 referrals per month from ACS meeting our eligibility criteria. Screening, on average, 13 veterans every month for 14 months equals 182 potentially eligible participants. We realistically estimate that 4-5 of these 13 potentially eligible veterans will consent to join the study, therefore we will be able to recruit and randomise 60 participants in 15 months.

We will offer a £15 high street voucher as a *thank you* to all participants who complete each of the 6, 12, 20 and 52 week questionnaire booklets. The maximum voucher value will be £60 per participant.

The veteran community is well-networked, and messaging about the trial aims and procedures must be well thought out and transparent to limit misinformation affecting recruitment and consent to randomisation (see appendix 2 for Stakeholder engagement protocol).

